#### **6.4 Study Intervention Compliance**

When participants self-administer study intervention(s) at home, compliance with study intervention will be assessed at each visit. Compliance will be assessed by review of daily diary entries and confirmatory capsule counts during study visits and documented in the source documents and relevant form. Deviation(s) from the prescribed dosage regimen should be recorded.

A record of the quantity of study intervention dispensed to and administered by each participant must be maintained and reconciled with study intervention and compliance records. Intervention start and stop dates, including dates for intervention delays will also be recorded. If the participant is unable to continue taking the study intervention as required, she should contact the study site.

#### **Study drug intake documenting**

Participants will document the number of study medication capsules taken, together with the HFDD evening diary once daily at bedtime using the 'Study drug intake documentation' on the electronic hand-held device during the treatment period as indicated in the SoA.

#### **6.5 Dose Modification**

Not applicable, all participants receiving active treatment will stay on the same dose.

#### **6.6 Continued Access to Study Intervention after the End of the Study**

No access to study intervention is planned after the end of the study.

#### **6.7 Treatment of Overdose**

For this study, any dose of elinzanetant greater than 240 mg within a 24-hour time period will be considered an overdose.

There is no known specific treatment (no antidote) for an overdose with elinzanetant. An overdose should be treated as clinically indicated based on signs and symptoms.

Overdose *per se* will not be reported as an AE and/or SAE unless it is associated with clinically relevant signs and/or symptoms, or an intentional overdose taken with possible suicidal and/or self-harming intent (see Sections 10.3.1 and 10.3.2).

In the event of an overdose, the investigator should:

- Contact the Sponsor immediately.
- Evaluate the participant to determine, in consultation with the Medical Monitor, whether study intervention should be interrupted or whether the dose should be reduced.
- Closely monitor the participant for any AE/SAE and laboratory abnormalities until stabilization and/or resolution.
- Obtain a plasma sample for PK analysis as soon as possible from the date of the last dose of study intervention if requested by the Medical Monitor (determined on a case-by-case basis).
- Document the quantity of the excess dose as well as the duration of the overdose in the eCRF.

Decisions regarding dose interruptions will be made by the investigator in consultation with the Medical Monitor based on the clinical evaluation of the participant.

## 6.8 Concomitant Therapy

Any medications (including over-the-counter or prescription medicines, contrast media, vaccines), vitamins and/or herbal supplements that the participant uses during the study participation must be recorded along with:

- Reason for use
- Dates of administration including start and end dates
- Dosage information including dose and frequency

The Medical Monitor should be contacted if there are any questions regarding concomitant or prior therapy.

### 6.8.1 Prohibited concomitant medications

Section 10.6 presents a comprehensive (but not exhaustive) list of prohibited concomitant medications (recently approved drugs may not be included in the list and should be checked on a case-by-case basis). The Medical Monitor should be contacted if there are any questions regarding concomitant or prior therapy.

Participants are permitted to continue to use antidepressant drugs and over the counter/herbal treatments when the dose has been stable for at least 4 weeks and when it is anticipated to be stable for the duration of the study. In addition, the drug has been prescribed solely for the management of another disorder (e.g. neuropathic pain, depression) (see Section 10.6 for further information).

### 6.8.2 Other Treatment Considerations

Based on preclinical data, an increase in exposure of drugs that are sensitive substrates of OATP1B1/1B3, P-gp or BCRP during co-administration of elizanetant due to inhibition of those transporters by elizanetant could not be excluded. Results from a clinical drug-drug interaction study with BCRP and OATP1B1/B3 substrate rosuvastatin showed no clinically

relevant effect on the pharmacokinetics of rosuvastatin when administered together with elinzanetant. Therefore, medications that are substrates of BCRP and/or OATP1B1/1B3 can be administered together with elinzanetant without restrictions.

In the absence of clinical drug-drug interaction data with P-gp substrates including but not limited to fexofenadine, dabigatran, digoxin, the following precautionary measures have to be implemented: Participants receiving a combination of elinzanetant and P-gp substrates should be closely monitored for signs and symptoms of adverse events due to increased exposure of the co-administered P-gp substrate. Dose modification of sensitive P-gp substrates should be considered based on the prescriber information or such compounds should be avoided.

### **Vitamin D and calcium supplements**

Postmenopausal women should take sufficient Vitamin D and Calcium (e.g. by food or supplement intake). 400 IU vitamin D, along with 500 mg to 1000 mg of calcium daily during the study period is considered sufficient. Investigators and study coordinators will be trained on the importance of vitamin D and calcium use. Participants will be counseled at every visit on the importance of taking vitamin D and calcium during the treatment period. If necessary, the dose of calcium or vitamin D supplementation may be modified or discontinued at the discretion of the investigator. The intake of vitamin D and calcium should be documented on the concomitant medication eCRF throughout the study.

## **7. Discontinuation of Study Intervention and Participant Discontinuation/Withdrawal**

### **7.1 Discontinuation of Study Intervention**

It may be necessary for a participant to permanently discontinue study intervention. If study intervention is permanently discontinued, the participant will be asked to remain in the study without receiving the study intervention until Visit T9 has been reached. As a general rule, all procedures scheduled for the end-of-treatment visit should be performed at the time of premature discontinuation of study intervention and documented. In case this is considered not medically appropriate for certain procedures (e.g. for invasive procedures if only short time has elapsed since the last scheduled assessment) this should be documented by the investigator. All scheduled study visits and procedures, except for study intervention, should continue if agreed by the participant. PK sampling is also not required. For participants who agree to continue in the study, any medication used after discontinuation of study intervention must be documented.

For withdrawal from study see Section [7.2](#).

#### **7.1.1 Liver Chemistry Stopping Criteria**

Discontinuation of study intervention for abnormal liver tests is required by the investigator when a participant meets one of the conditions outlined in Section [10.5](#) or in the presence of abnormal liver chemistries not meeting protocol-specified stopping rules if the investigator believes that it is in best interest of the participant. See Section [10.5](#) for further details.

### 7.1.2 Platelet count Stopping Criteria

In the case of platelet counts below  $50,000/\text{mm}^3$ , study intervention must be discontinued immediately. In the case of platelet counts between  $50,000/\text{mm}^3$  and  $75,000/\text{mm}^3$ , a retest should be performed within 72 hours of the initial test results. If values do not normalize within 7 days, study intervention must be discontinued.

### 7.1.3 Temporary Discontinuation

In the event that a participant experiences an AE which the investigator believes is treatment related and which the participant finds intolerable, a break in dosing of up to one week is permitted. If, on reintroduction of the study medication, the AE recurs and remains intolerable, the study drug will be permanently withdrawn. A break in dosing will not result in extension of the overall dosing period.

Temporary discontinuation is also allowed in the following two cases:

- Temporary discontinuation of study intervention for an intercurrent illness, at the discretion of the investigator.
- In the event of a trial-continuity issue (e.g. caused by a pandemic), the sponsor may provide additional guidance in study-specific communication.

### 7.1.4 Rechallenge

Study intervention may be restarted after a temporary interruption if deemed clinically appropriate by the investigator in collaboration with the Sponsor's Medical Monitor.

#### 7.1.4.1 Study Intervention Restart or Rechallenge After Liver Stopping Criteria Met

Study intervention restart or rechallenge after liver chemistry stopping criteria are met by any participant in this study is not allowed.

## 7.2 Participant Discontinuation/Withdrawal from the Study

- A participant may withdraw from the study at any time at her own request, or may be withdrawn at any time at the discretion of the investigator for safety, behavioral, or compliance reasons.
  - If a participant is tested positive for SARS-CoV-2 infection while on study, the investigator will have to decide whether staying in the study is compatible with participant and site personnel safety and wellbeing. In most cases, temporary discontinuation (see section 7.1.3) may be an appropriate solution. The decision should also take into account possible interaction between the study intervention and potential treatment for SARS-CoV-2 infection.
- At the time of discontinuing from the study, if possible, an End of Treatment visit procedures should be conducted, followed by FU visit as shown in the SoA and in particular described in footnote a) in [Table 1-2](#).

- Participants who have been randomized but not yet started study intervention do not need to undergo further study procedures other than return of supplies, before their study participation terminates.
- For withdrawal during the follow-up period, the participant should undergo the assessments scheduled for the next visit (FU Visit)
- The participant will be permanently discontinued both from the study intervention and from the study at that time.
- If the participant withdraws consent for disclosure of future information, the sponsor may retain and continue to use any data collected before such a withdrawal of consent.

For Withdrawal from study intervention see Section [7.1](#)

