**Table 3–2 : Primary Estimand: ICEs and Strategies to Address Them**

ICEs a	Reason for ICE	Strategy	Data handling method
Temporary Treatment interruptionb	AEs (treatment related/unrelated)	Treatment policy	Utilise the collected data after ICE.
	COVID-19 and administrative reasons	Treatment policy	Utilise the collected data after ICE.
Permanent discontinuation of randomized treatment	AEs (treatment related/unrelated) or Lack of efficacy		
	For participants who remained untreated/on background therapy.	Treatment policy	Utilise the collected data after ICE.
	For participants who initiate alternative VMS treatment	Treatment policy	Utilise the collected data after ICE.
Intake of prohibited concomitant medication having impact on efficacy	Other treatment-unrelated reasons, including COVID-19	Treatment policy	Utilise the collected data after ICE.
	All reasons	Treatment policy	Utilise the collected data after ICE.

AE = Adverse event, COVID-19 = Coronavirus disease of 2019, ICE = Intercurrent event, VMS = Vasomotor symptoms

a) ICEs will be reviewed at the Blinded Review Meeting prior to the study unblinding.

b) Definition of temporary treatment interruption: Week 12= Treatment taken <80% during weeks 1-12 OR treatment taken on <5/7 days during either week 11 or 12.

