SAS code:	<pre>PROC MIXED data=DATA;   CLASS subject treatment region week;   MODEL change = baseline treatment region week     treatment*week baseline*week/ddf=KR outp=resid s;   REPEATED week / subject=subject type=un;   RANDOM subject; /* only if AR(1) covariance structure is used */   LSMEANS treatment*week /cl diff;   ESTIMATE 'Elinzanetant - Placebo at Week 12' treatment 1     -1 treatment*week 0 0 0 1 0 0 0 -1 /cl;   ODS OUTPUT TESTS3=TYPE3_eff LSMeans=LSMEAN   ESTIMATES=ESTIM;   RUN;</pre>

A treatment policy strategy will be applied to handle all of the ICEs in this trial in the main estimand. According to this policy, all collected data should be utilized in the analysis irrespective of occurrence of the ICEs.

Although all study participants are expected to be followed after ICEs, some missing data may occur. Missing values that occur while participants continue on their randomized treatment and simply represent missed assessments will be assumed missing at random (MAR). Such missing values are likely to be intermittent and will be imputed using a Monte Carlo Markov Chain (MCMC) MI method for imputation of non-monotone missing data. For the baseline value to be imputed, at least 2 post-baseline values out of the 4 post-baseline values (i.e. Week 1, 4, 8 & 12) need to be available. Possible missing baseline values will be

imputed together with intermittent missing values. Absolute values will be used for imputation steps.

Missing values that occur after the discontinuation of randomized treatment will be imputed using a multiple imputation (MI) model (Rubin, 1987) such that it aligns with the treatment policy estimand. The MI regression model will include auxiliary variables indicating (yes/no) whether the participant continued on randomized treatment at each visit (i.e. Week 1, 4, 8 & 12). These variables will be included in the imputation model to account for the occurrence of permanent discontinuation of randomized treatment (Guizzaro et al., 2021). In addition to the indicator variables, baseline HF, region and treatment as specified in [Table 5–3](#) as well as previous post-baseline endpoint values will also be included in the imputation model. In case, there are less than 10 participants (who permanently discontinued the randomized treatment) across both treatment groups with available post-discontinuation data at any intermediate time point, the indicator variable will not be included in the imputation model for that time point.

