### **6.5.2 Permanent discontinuation of randomized treatment**

The reasons for permanent discontinuation of randomized treatment will be collected on the corresponding eCRF page, among others with AE or lack of efficacy as possible options. A permanent discontinuation of randomized treatment will be considered to be due to “other treatment unrelated reasons” if AE or lack of efficacy was not selected as reason and any of the following was selected:

- Non-compliance with study device
- Site terminated by sponsor
- Technical problems
- Pregnancy
- Subject decision
- Subject decision: unwillingness to comply with study procedures
- Lost to follow-up
- Other
- COVID-19 pandemic related: subject specific
- COVID-19 pandemic related: other
- Non-compliance with study drug
- Randomized by mistake
- Withdrawal by subject

The observed permanent discontinuations of randomized treatment together with corresponding reason will be presented in data listings.

Discontinuation due to AE or lack of efficacy may be handled differently depending on estimand for participants who remained untreated/background therapy and for participants who initiate alternative VMS treatment. The treatment status (i.e., remained untreated/on background therapy vs. initiate alternative VMS treatment) should be captured for all participants who discontinued from randomized drug irrespective of the reason for

discontinuation.

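### Protocol 7.2 lets an investigator end study follow-up for compliance reasons without excluding drug non-compliance, so off-treatment diary data that the primary estimand would use may never be collected

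*Protocol*

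**What the plan says.** Protocol 7.2 deals with leaving the study, as distinct from stopping drug. A woman may leave at her own request, "or may be withdrawn at any time at the discretion of the investigator for safety, behavioral, or compliance reasons". The section adds: "The participant will be permanently discontinued both from the study intervention and from the study at that time". It does not define compliance, and it does not separate missed capsules from missed visits or diary entries.

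Protocol 7.1 deals with stopping drug only. There, "the participant will be asked to remain in the study without receiving the study intervention until Visit T9 has been reached", and scheduled visits and procedures (other than dosing and PK sampling) go on if she agrees.

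Protocol Table 3-2 and SAP Table 1-2 assign treatment policy to each listed ICE, with the instruction "Utilise the collected data after ICE". Footnote b of Table 3-2 defines temporary interruption for Week 12 purely by intake: "Treatment taken <80% during weeks 1-12 OR treatment taken on <5/7 days during either week 11 or 12". SAP 5.3.1 leaves no exception: "A treatment policy strategy will be applied to handle all of the ICEs in this trial in the main estimand". It then says: "Although all study participants are expected to be followed after ICEs, some missing data may occur".

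SAP 6.5.2 lists "Non-compliance with study drug" among the reasons for permanently stopping randomized treatment, in the treatment-unrelated group.

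**The concern.** Poor drug intake is one of the behaviours that the primary estimand says to follow through, and 7.2 allows follow-up to end because of it. The primary outcome comes from a home eDiary, and Protocol 9.4.1 notes that it does not depend on clinic attendance. A woman who misses capsules can still report hot flashes. If the investigator withdraws her from the study, her Week 12 value is imputed, although it might have been observed.

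Such missing values relate to adherence and so, plausibly, to outcome. They also depend on a discretion that can differ between sites. The primary analysis has most to lose. When a woman stops drug for a treatment-unrelated reason, which under SAP 6.5.2 includes non-compliance with drug, both supplementary estimands discard what follows. Only the primary analysis would use her off-treatment values. Her observed data would also help to inform the imputation of other women who stopped drug and have missing values.

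**Working it through.** **1. The passages side by side**

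- Woman stops drug, stays in the study (Protocol 7.1): follow-up to T9 is requested, and her data are used under treatment policy.
- Woman takes too little drug (Table 3-2, footnote b): this is an ICE, and her data are used under treatment policy.
- Woman takes too little drug and the investigator withdraws her from the study (Protocol 7.2): follow-up ends, and later values are imputed under SAP 5.3.1.

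The second and third cases can concern the same woman. Only the investigator's choice decides which applies.

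**2. The plan's own figure**

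Inputs (Protocol 9.2, Table 9-1): 300 per arm, 10% drop-out to month 3, SD 4.29, one-sided 0.025.

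- n = 300 × 0.90 = 270 per arm.
- Non-centrality at a difference of 1.00 = 1.00 / (4.29 × √(2/270)) = 2.71, with 538 degrees of freedom.
- Power = 77.1%, as stated. The figures at 1.50 and 2.00 also reproduce (98.2% and above 99.9%).

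**3. How many women (assumption)**

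The documents give no rate of withdrawal for compliance. Suppose 10-30% of early drop-outs are of this kind.

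- Early drop-outs: 0.10 × 300 = 30 per arm.
- Affected: 3 to 9 per arm, or 1-3% of 300.

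**4. Power**

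If these women are part of the planned 10%, power is unchanged. If instead 2% of each arm were lost on top of it, n = 300 × (1 − 0.10 − 0.02) = 264 and power at 1.00 falls from 77.1% to 76.2%.

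**5. Bias**

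Suppose a fraction w of the elinzanetant arm is imputed as if still on drug, while the true off-drug effect is zero. The difference is then overstated by w × effect.

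- Effect 1.00: 0.01 × 1.00 = 0.01 to 0.03 × 1.00 = 0.03 hot flashes per day.
- Effect 2.00: 0.02 to 0.06.

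This is an upper figure under that assumption, because the imputation model is designed to separate on-drug from off-drug values.

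**6. The imputation indicator**

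SAP 5.3.1 drops the on-treatment indicator at an intermediate time point if fewer than 10 discontinued women across both arms have data there. Assume 10% of 600 women discontinue drug at a constant rate over 12 weeks, so the number by a given week is 60 × week/12.

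| Week | Discontinued, both arms | Left if 10-30% are withdrawn from the study |
|---|---|---|
| 1 | 5 | below 10 in any case |
| 4 | 20 | 14-18 |
| 8 | 40 | 28-36 |

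If the other women keep reporting, the indicator survives at Weeks 4 and 8. At Week 4 it would be dropped only if more than half of the 20 had no data.

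**The case against.** The case on the other side is substantial, and most of it limits the point.

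- A reader might infer that 7.2 deletes data that the estimand promised to use. It does not. The estimand refers to collected data, nothing collected is discarded from the main analysis, and a withdrawn woman stays in the full analysis set of all randomized participants. The loss is of data never collected.
- A reader might take the SAP 6.5.2 list as proof that withdrawal from the study for non-compliance is expected. That list gives reasons for stopping treatment. A woman recorded there falls under 7.1 and is asked to stay.
- Compliance in 7.2 may mean compliance with procedures. A woman who does not complete procedures might not supply a Week 12 diary either. Drug intake is logged on the same device as the evening diary, so the two kinds of non-compliance may coincide. This stands, and is why the point is confined to drug non-compliance alone.
- Retention is already the default. Withdrawal under 7.2 is optional, Table 2-1 encourages women who stop drug to remain, and footnote a of Table 1-2 separates stopping drug from leaving the study. This stands too, but none of these texts restricts the discretion in 7.2.
- The gap has planned handling: multiple imputation with on-treatment indicators, and a tipping-point analysis that shifts values imputed within an ICE in the elinzanetant arm (SAP 5.3.2.2 and 6.4). These handle and probe the missing values; they do not replace an observation that could have been made.

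**Conclusion.** The point holds as a narrow conflict over data collection. Section 7.2 leaves room to end follow-up for a behaviour that the primary estimand says to follow through, against 7.1 and against the SAP's expectation of follow-up after ICEs. The result is avoidable missing data related to adherence.

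Its likely size is small: 0.01-0.03 hot flashes per day at an effect of 1.00, and no power cost if the women fall within the planned drop-out. This rests on an assumed 1-3% of an arm, for which the documents offer no source, and on a zero off-drug effect. A reader might go further and infer that these withdrawals would disable the imputation indicator or threaten the primary conclusion. On these assumptions, they would not do so by themselves. The case for change is that the remedy is cheap and brings conduct into line with the estimand.

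**What to change.** Reconcile Protocol 7.2 with 7.1, Table 3-2 and SAP 5.3.1 by adding one sentence to 7.2. It should say that non-compliance with study drug alone is not a reason to end study follow-up, and that diary and scheduled assessments continue as described in 7.1 if the participant agrees.

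The change concerns data collection only. Safety grounds, the participant's own right to withdraw, inability or unwillingness to follow study procedures, and every treatment-stopping rule stay as written.

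The cost is a short protocol amendment, which needs ethics approval under Protocol 10.1.1, a reminder to sites, and a few more diary weeks from women already enrolled. The sample size and the SAP models need no change.
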